3.7 Distributional Assumption Tests

Empirical distributions of all variables will be visually inspected to detect outliers. The underlying proposed statistical methods for each analysis will be examined, primarily through inspection of graphical displays, standardized residuals, or influence diagnostics. Where appropriate,

transformations will be utilized or analyses will be performed utilizing a more appropriate distribution.

4.0 ANALYSES OF DEMOGRAPHIC AND BASELINE DATA

The demographic variables for this study include: gender, age, race, ethnicity, education level, employment status, and marital status. The baseline clinical characteristics include: opioid dependence severity, severity of other substance use, severity of mood/anxiety symptoms, severity of opioid withdrawal symptoms, current/past co-occurring psychiatric disorders, current medical disorders, select genetic markers, history of legal problems, currently under legal supervision (parole, probation or mandated).

Descriptive statistics for baseline and demographic variables will be presented for participants randomized to each of the treatment arms and overall. Descriptive statistics will include N, mean, standard deviation, median, 25th and 75th percentiles, minimum and maximum for continuous variables and proportions and percentages for categorical variables. Since randomization is expected to produce balance at baseline between the two arms of the trial, statistical comparisons of treatment groups with respect to baseline characteristics will not be conducted. The updated CONSORT statement no longer recommends formal testing of statistical significance of differences between baseline characteristics.

5.0 STATISTICAL ANALYSES

5.1 Timing of Randomization Definitions

The early randomizers are those participants randomized within 72 hours following the last licit or illicit opioid use. The late randomizers are those participants randomized greater than 72 hours following the last licit or illicit opioid use. To determine the timing of randomization, it is necessary to know the day and time (measured using 24 hour clock) of last licit or illicit opioid use. On rare occasions, missing values for one or both of these measures may exist. For primary analysis purposes, if the date of last licit or illicit opioid use is available but the time is not, the participant's time will be imputed to be 00:00. This will impute the longest potential time from randomization. If the date of last licit or illicit use is missing, the participant categorization will be imputed by the predominant proportion of the randomization timing status in that site.

5.2 Differential Treatment Initiation for Early Randomizers Assessment

The study modification assessment will be completed when the 100 participants who have been randomized within 72 hours following his/her last (licit or illicit) opioid use have had at least 21 days post-randomization to be inducted onto study medication. The analysis population for the early randomizers assessment will only consist of the first 100 early randomizers. The timing of the database freeze will ensure that these 100 early randomizers have had at least 21 days post-randomization to be inducted onto study medication.

5.2.1 Induction Status Determination

A participant's induction status will be a binary variable of Yes or No. For the participants randomized to BUP-NX, participants will be defined as inducted onto the study medication if he/she has been dispensed medication as measured on the BUP-NX dose log; otherwise, the participant will be defined as not being inducted onto study medication. In a similar manner, for participants randomized to XR-NTX, participants will be defined as inducted onto the study medication if he/she has received an injection of the study medication. Note, the definition of induction status is not dependent upon the number of days for induction to occur.

5.2.2 Induction Status Analysis

The null hypothesis is:

$$H_0 : p_{XR-NTX} = p_{BUP-NX}$$

$$H_A : p_{XR-NTX} \neq p_{BUP-NX}$$

Where p_{XR-NTX} is the proportion of early randomizer participants in the XR-NTX group who were inducted and p_{BUP-NX} is the proportion of early randomizers participants in the BUP-NX group who were inducted. The Fisher's exact test will be used to determine statistical significance at a significance level of 0.05.

5.3 Primary Outcome

The primary outcome measure will be the time to the event, with the event called relapse. By definition individuals are abstinent at the time of randomization. Relapse occurs if the participant is using any non-protocol prescribed opioids regularly starting at day 21 post-randomization or thereafter. Operationally, loss of persistent abstinence is defined as either: (a) four consecutive opioid use weeks, or (b) seven consecutive days of use by self-report. A use week is defined as any week during which a participant self-reports at least one day of use during that week, provides a urine sample positive for non-protocol opioids, or fails to provide a urine sample.

Self-report of opioid (heroin or prescription opioids) and other substance use will be ascertained at each weekly study visit using the Time Line Follow-back for each day leading back to the previous visit. Urine will be collected at each study visit and tested for opioids. In the event that a participant reports no use, but their urine test indicates use, then we will regard the week as a use week. Missing urine samples will be classified as positive. The time of the event occurs at the start of the qualifying clinical event period (e.g., first of the 7 consecutive use days or start of the 4 consecutive weeks of use).

5.3.1 Primary Outcome Criteria

Relapse assessment starts Day 21 post-randomization with the day of randomization as Day 0 and ends at the Week 24 visit. As noted above, relapse is defined in two ways:

- a) Four consecutive opioid use weeks
 - i) There are three ways that a use week can be established:
 - (1) Participant self-reports at least one day of use during that week

The self-report of use is measured between the weekly visits and thus does not always include the review of exactly seven days. At the weekly visit, if the previous visit was missed, the participant's daily self-report opioid use is assessed from the start of the current visit window (i.e. the beginning of the window as specified by the protocol calendar, see table below) to the day before the current visit. Conversely, if the previous visit was attended, the participants daily self-report opioid use is assessed from the previous visit attended day to the day before that current visit. Note, only participants self-report collected on or after Day 21 is used in evaluating whether the week is a use week. Thus, if the Week 3 visit is attended on Day 21, there cannot be a use week based on self-reported opioid use.

Visit Number	Target Day	Beginning Window (Days)	End of Window (Days)
00R	00	00	00
01	06	3	12
02	13	10	16
03	20	17	23
04	27	24	30
05	34	31	37
06	41	38	44
07	48	45	51
08	55	52	58
09	62	59	65
10	69	66	72
11	76	73	79
12	83	80	86
13	90	87	93
14	97	94	100
15	104	101	107

Table 3: CTN-0051 Protocol Calendar			
Visit Number	Target Day	Beginning Window (Days)	End of Window (Days)
16	111	108	114
17	118	115	121
18	125	122	128
19	132	129	135
20	139	136	142
21	146	143	149
22	153	150	156
23	160	157	163
24	167	164	195

(2) Participant provides a urine sample positive for non-protocol opioids

The urine drug screen (UDS) is used to assess whether the urine sample is positive for non-protocol opioids. Only UDSs assessed at weekly visits will be used to determine relapse status. UDSs assessed at the inductions that occur prior to Day 21, supplemental induction or end of treatment visits will not be used to assess relapse. Note, any induction UDSs that occur after Day 21 are entered into the weekly visit, and the results are duplicated in the induction visit UDS. Additionally, supplemental UDSs are not expected and should not be entered except for supplemental induction visits. If an out of window visit occurs, the UDS collected at that out of window visit will contribute to the use week calculation of that visit.

For the BUP-NX arm, use for a urine sample is defined as a positive result for any of the following tests: Opiates (2000 ng), Oxycodone (OXY), Methadone (MTD), or Opiates (300 ng). For the XR-NTX arm, use for a urine sample is defined as a positive result for any of the following tests: Opiates (2000 ng), Oxycodone (OXY), Methadone (MTD), Opiates (300 ng) or Buprenorphine (BUP).

(3) Participant fails to provide a urine sample.

UDSs that are not collected, determined to be adulterated or out of the temperature range result in a use week. If the field indicating adulterated or out of temperature range is missing, that UDS would result in a use week. Additionally, missed visits are tracked using the missed visit form. If the missed visit form is completed, that week is designated a use week.

b) Seven consecutive days of use by self-report

The timeline follow back dataset is used to calculate the number of consecutive use days. A use day is defined as values for the opioids mentioned above. The first instance of seven consecutive days of use by self-report will define the participant as relapsed. The first day of the seven consecutive days is defined as the relapse start date.

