and followed as outpatients until 24 weeks post-randomization. Assessment visits occur weekly until relapse criteria are met. Participants whose induction onto their assigned study medication is delayed will also attend weekly research visits. Medical management visits will initially occur weekly, transition to every two weeks and then to every four weeks. In order to retain participants in treatment, and consistent with good practice, we permit flexibility with dosing (see section 8.5). The window for Visit 1 is -3/+6 days to accommodate induction; however, induction may occur after Visit 1. A +/- 3-day window is permissible for subsequent weekly visits. For participants who relapse and/or become lost to follow up, a -3/+28 day window is permissible to complete the EOT visit. Participants who relapse will discontinue study medication and weekly research visits, but should be encouraged to attend the week 24 and follow up visits at weeks 28 and 36.

Phase 4: Post Treatment Follow-up (Week 25 through Week 36): Toward the end of the 24-week treatment period, participants are referred for follow-up care in the community (which could include continuation of medication, if available, indicated, and desired), and follow-up outcomes are assessed at week 28 and week 36 post-randomization. For participants receiving BUP-NX, who do not wish to continue, or for whom community resources are not available, the study provides a two-week BUP-NX taper. A -3/+28 day window is permissible for the scheduled week 28 visit and a +/- 4 week window is permissible for the scheduled week 36 visit.

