Both groups receive Medical Management (MM) clinical support from the same study clinicians (e.g., MD, DO, PA, NP, RN; working within the scope of their local licensure, clinical privileges and/or scope of practice) in unblinded fashion. MM is adapted from several recent studies of NTX, XR-NTX and BUP-NX, including the NIAAA COMBINE study⁶³, Krupitsky et al.⁸, and CTN-0030 (POATS).⁵⁷ Briefly, MM sessions focus on establishing and maintaining patient-clinician rapport and partnership, education surrounding opioid addiction and treatment, establishing and maintaining a plan for XR-NTX or BUP-NX medication adherence, advice and encouragement to maintain abstinence, monitoring medication side effects and dose adjustments, and support for ancillary treatment, including weekly psychosocial counseling, 12-step involvement, and further community-based treatment. MM also provides guidelines for assessment and management of relapse in both arms. In contrast to studies specifically analyzing the effect of a trial's psychosocial interventions (i.e., the COMBINE trial or CTN-0030, POATS), and in keeping with a pragmatic, community-based comparative effectiveness trial, MM is broadly guided by provider training prior to study start and regular MM provider calls, a common progress note and the MM MOP, but is not subject to rigorous quality assurance procedures (i.e., audiotaping, manualization and QA audits). The study clinician assesses concomitant medications at each medical management visit. As this is not an IND study, and both medications are FDA approved for opioid dependence, the study data capture system does not include a concomitant medication case report form. MM visit schedules are the same for both arms, initially weekly (weeks 0-4), then every two weeks (weeks 4-16), and finally every four weeks (weeks 16, 20, 24). XR-NTX is injected at the MM visit approximately every 4 weeks with the final injection occurring no later than week 22. BUP-NX is dispensed at each MM visit through week 20. For all participants a final MM visit takes place on week 24 although no medication is dispensed (except for BUP-NX taper where this is indicated).

B. Psychosocial Counseling: Both Arms

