Phase 3: Active Treatment (Week 1 through Week 24): Following randomization, participants will be inducted as soon as practicable and treated per their assigned active medication condition and followed as outpatients until 24 weeks post-randomization. Assessment visits will occur weekly. Participants whose induction onto their assigned study medication is delayed will also attend weekly research visits. Medical management visits will initially occur weekly, transition to every two weeks and then to every four weeks. In order to retain participants in treatment, and consistent with good practice, we permit flexibility with dosing. The window for Visit 1 is -3/+6 days to accommodate induction; however, induction may occur after Visit 1. A +/- 3-day window will be permissible for subsequent weekly visits. For participants who relapse and/or become lost to follow up, a -3/+28 day window is permissible to complete the EOT visit. Participants who relapse will discontinue study medication and weekly research visits, but should be encouraged to attend the week 24 and follow up visits at weeks 28 and 36.

Phase 4: Post Treatment Follow-up (Week 25 through Week 36): Toward the end of the 24-week treatment period, participants will be referred for follow-up care in the community (which could include continuation of medication, if available, indicated, and desired), and follow-up outcomes will be assessed at week 28 and week 36 post-randomization. For participants receiving BUP-NX, who do not wish to continue, or for whom community resources are not available, the study will provide a two-week BUP-NX taper (beginning at the week 24 visit). A -3/+28 day window will be permissible for the scheduled week 28 visit and a +/- 4 week window will be permissible for the scheduled week 36 visit.

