¹ Injection intervals are defined as time between two consecutive injections. To have an injection interval, participants must have at least two injections. Participants with more than two injections will have multiple injection intervals included.

Table 13: Summary of BUP-NX Prescribed Daily Dose by CTP

	OV Maryhaven	FL Gateway Community Services	PA Tarzana Treatment Centers	NEC Stanley Street Treatment and Resources (SSTAR)	GNY Bellevue Hospital Center	PNW ETS/RCKC	MA Avery Road	SW Turquoise Lodge Hospital	Total
Number of Participants Randomized to BUP-NX									
Maximum Prescribed Daily Dose Across all Visits									
N									
Mean									
SD									
Median									
Min									
Max									
Minimum Prescribed Daily Dose Across all Visits									
N									
Mean									
SD									
Median									
Min									
Max									

Figure 6: Participant-level Prescribed Daily Dose of Buprenorphine

Example figure provided.

Table 14: Availability of Primary Outcome by Treatment Arm (Day 21 – Day 167*)

Treatment Arm	Participants Randomized	Number of UDS Collected	Number of UDS Expected	Percentage of UDS Collected	Number of TLFB Days Collected	Number of TLFB Days Expected	Percentage of TLFB Days Collected	Availability of Primary Outcome**
BUP-NX								
XR-NTX								
Total								

*Day 167 or the last day of the relapse event, whichever occurs first, for participants who have been inducted onto study medication.

**The Availability of Primary Outcome is the average of the percentage of expected TLFB days collected and percentage of expected UDS collected.

Table 15: Summary of Primary Outcome (Relapse) by Treatment Arm			
	Treatment Arm		
	BUP-NX (N=)	XR-NTX (N=)	Total (N=)
Relapse Status ¹			
Yes			
No			
Time to Relapse ² (days)			
Mean			
SD			
Median			
Min			
Max			
Percentage of Opioid Use Days based on TLFB ³ (Day 0-21 post-randomization) (%)			
Mean			
SD			
Median			
Min			
Max			
UDS Result at Randomization (Day 0)			
Positive for non-prescribed Opioids			
Negative for non-prescribed Opioids			
Missing			
UDS Result at Week 1 (Day 3-12)			
Positive for non-prescribed Opioids			
Negative for non-prescribed Opioids			
Missing			
UDS Result at Week 2 (Day 10-16)			
Positive for non-prescribed Opioids			
Negative for non-prescribed Opioids			
Missing			
UDS Result at Week 3 (Day 17-23)			
Positive for non-prescribed Opioids			
Negative for non-prescribed Opioids			
Missing			

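### Relapse derivation has no fixed closing day: visit 24 may fall as late as Day 195, so self-reported use after Day 167 can count as a 24-week relapse

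*SAP*

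**What the plan says.** The endpoint is closed by a visit, not by a day: "Relapse assessment starts Day 21 post-randomization with the day of randomization as Day 0 and ends at the Week 24 visit" (SAP 5.3.1). The footnote to SAP Appendix A Table 15 likewise judges a participant not relapsed by reference to the Week 24 visit. SAP 5.3.3 names STATUS as the censoring variable but gives no censoring day.

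The visit windows disagree. SAP Table 3 gives visits 2 to 23 a window of 3 days either side of target, and gives visit 24 Day 164 to Day 195 with no restriction on who may use it. The text reads differently. Protocol 6.1 says "A +/- 3-day window is permissible for subsequent weekly visits", and SAP 1.2 says "A +/- 3-day window will be permissible for subsequent weekly visits". The long window is kept for a subgroup and a different visit: "For participants who relapse and/or become lost to follow up, a -3/+28 day window is permissible to complete the EOT visit" (Protocol 6.1, repeated in SAP 1.2).

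Three rules in SAP 5.3.1 decide what a late visit contributes:
- Self-report for a use week runs to the day before the visit. If the preceding visit was missed, "the participant's daily self-report opioid use is assessed from the start of the current visit window".
- A urine taken out of window still counts: "the UDS collected at that out of window visit will contribute to the use week calculation of that visit". The same paragraph excludes urines taken at end-of-treatment visits.
- The seven-day criterion takes the first qualifying run in the timeline follow-back data and states no last day.

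Elsewhere the SAP works to a fixed end. The shell for availability of the primary outcome (Appendix A, Table 14) stops at "Day 167 or the last day of the relapse event, whichever occurs first".

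**The concern.** The objective is time to relapse during the 6-month trial, and SAP 5.3.3 also asks for success rates at week 24. Both need every participant to be at risk over the same calendar. If the last countable day depends on when someone turns up, two participants with the same use can receive different event status. Late attendance is also unlikely to be random in this population. The extra days lie after the 24-week treatment phase, so events found there do not belong to the stated endpoint.

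**Working it through.** **Inputs.** Visit targets and windows: SAP Table 3. Use-week, seven-day and urine rules: SAP 5.3.1. Event dating: SAP Table 4. Week-28 visit: Day 195 in the Protocol's schedule of assessments, window -3/+28 (Protocol 6.1). Success rate of 40% with exponential failure: SAP 3.3.

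**1. Reproduce Day 195.** Target of visit k = 6 + 7(k - 1). For k = 24: 6 + 161 = 167. Applying -3/+28 gives 164 to 195, which is the Table 3 row. Applying 3 days either side gives 164 to 170. The window is therefore 195 - 164 + 1 = 32 days instead of 7. Visit 23 (target 160, window 157 to 163) follows the 3-day rule.

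**2. Self-report.** For a visit on day v, the last countable day is v - 1, and the latest start of a seven-day run is v - 7.

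| Visit 24 on | Days covered, visit 23 missed | Days covered, visit 23 on Day 160 | Latest seven-day start |
|---|---|---|---|
| Day 167 | 164 to 166 | 160 to 166 | 160 |
| Day 170 | 164 to 169 | 160 to 169 | 163 |
| Day 195 | 164 to 194 | 160 to 194 | 188 |

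Up to 194 - 167 = 27 self-report days after Day 167 can enter. Take two participants who both use on Days 170 to 176. The one seen on Day 167 has no event. The one seen on Day 195 has a relapse dated Day 170.

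**3. Urine.** Suppose weeks 21, 22 and 23 are use weeks because the visits were missed. Status then turns on week 24:

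| What happens at week 24 | Week 24 | Relapse by criterion (a) |
|---|---|---|
| No urine by Day 170, later urine not counted | use | yes, dated Day 143 |
| Day 190, negative, no reported use, urine counted | not use | no |
| Day 190, positive | use | yes, dated Day 143 |
| Day 190, negative, one reported use day (Day 185) | use | yes, dated Day 143 |
| Day 190, negative, visit classed as end of treatment | missing, so use | yes, dated Day 143 |

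Day 143 is the start of the week-21 window, which Table 4 assigns when the first use week is a missing urine alone. Compared with a strict Day 164 to 170 rule, the long window can only cancel a relapse by this route. Narrowing the Table 3 row would not be enough, because the out-of-window sentence would still admit the later urine.

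**4. Overlap.** The week-28 window is 195 - 3 = 192 to 195 + 28 = 223. On Days 192 to 195 the visit label alone decides whether the data belong to the primary endpoint.

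**5. Size, as an illustration.** With 40% success at Day 167 and constant hazard, success by Day 194 is 0.4^(194/167) = 0.345, a drop of 5.5 points if everyone were followed that far. The documents give no share of late attenders. For assumed shares of 5%, 10% and 20% seen on Day 195, the drop is 0.05 × 5.5 = 0.28, 0.10 × 5.5 = 0.55 and 0.20 × 5.5 = 1.1 points. This applies the overall relapse hazard to late attenders, whereas only the seven-day route can add events, and it ignores cancelled relapses.

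**The case against.** The best defence is the SAP's own exclusion of urines from end-of-treatment visits. Someone who misses weeks 21 to 23 and returns weeks later may well count as lost to follow-up, so the late visit would be an end-of-treatment visit, its urine would not count and the relapse would stand. The Protocol supports both readings. It often writes week 24 and end of treatment as one visit (11.1.7 and 11.4.2, for example), but its schedule lists end of treatment in a separate column for use when it is not week 24. If the exclusion covered every week-24 visit, no week-24 urine could count, which sits badly with assessment ending there. So the cancellation is conditional. The exclusion concerns urine only and leaves the self-report problem untouched.

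A late returner is also not wholly unobserved. Protocol 11.4.1 collects each day since the previous follow-back, so a reported seven-day run in the gap still counts. That stands, and it limits cancellation to people who report no such run.

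Table 14 is a data-availability shell for inducted participants and does not define the endpoint. It shows only that the SAP elsewhere works to Day 167.

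A reader might infer a tilt against BUP-NX, because "BUP-NX is dispensed at each MM visit through week 20" (Protocol 8.5) while an XR-NTX injection may be given up to week 22, whose window ends on Day 156; 28 days of blockade would reach Day 184. The documents do not establish this. Protocol 8.5.3 allows a taper of up to two weeks from the week-24 visit (167 + 14 = Day 181), and Protocol 6.1 plans for continued medication in the community. SAP 5.3.1 counts a buprenorphine-positive urine as use only in the XR-NTX arm, which could work the other way.

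**Conclusion.** The point holds in limited form. The SAP does not fix when the primary endpoint closes, Table 3 conflicts with the window text of both documents, and use after Day 167 can be counted as a 24-week relapse solely because of the attendance date. Creation of events rests on the seven-day self-report criterion. Cancellation by a late negative urine is possible but depends on a visit classification that the SAP leaves open.

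A reader might also infer that a single late use day, after three missed weeks, creates a relapse dated back to Day 143. It does not: a missing week-24 urine gives the same event and date.

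The number affected is unknown and the overall effect is probably small. The illustrative figures rest on assumed shares and a constant hazard. No direction between arms is established, and sample size and power are unaffected. The correction is still worth making, because an affected participant's status can change outright.

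**What to change.** In SAP 5.3.1 and Table 3, close relapse derivation on the same study day for everyone:
- Count self-report for both criteria only through Day 167. A qualifying seven-day run then starts no later than Day 161 (167 - 6).
- Censor non-relapsers at Day 167, in line with Table 14.
- Count the week-24 urine only if collected on Days 164 to 170. State that a later urine leaves week 24 missing, hence a use week under the existing rule, as an explicit exception to the out-of-window sentence. This also settles the end-of-treatment ambiguity for late visits.
- Add a sensitivity analysis that counts the late urine.
- Keep the 28-day extension for the other end-of-treatment assessments.

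The cost is SAP wording, one programming condition and one sensitivity run; visit conduct does not change. The downside is that a few late week-24 urines and self-reports leave the primary outcome, and an observed late negative urine is set aside in the primary analysis. Urine and self-report would still close three days apart (Day 170 and Day 167), but on the same days for all participants.
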